#### Packs

Starting 4-week card: 0.5 mg × 11 tablets and 1 mg × 42 tablets NDC 00069-0471-03

Continuing 4-week card: 1 mg × 56 tablets NDC 00069-0469-03

Starting Month Box: 0.5 mg × 11 tablets and 1 mg × 42 tablets NDC 00069-0471-03

Continuing Month Box: 1 mg × 56 tablets NDC 00069-0469-03

#### Bottles

0.5 mg - bottle of 56 NDC 00069-0468-56

1 mg - bottle of 56 NDC 00069-0469-56

Medication will be labeled with the subject's study ID, "For Research Purposes", Study telephone number, Medication Name and strength, Instructions for use, Dispensed date, Expiration date, and Quantity. The research staff dispensing the medication will include their initials on the label and document the dispensation (and return of unused medication) on the product accountability log. Upon completion of the study or if the subject stops taking the medication, any medication that is returned by the subject will be taken to the pharmacy for appropriate disposal.

A general accounting of all varenicline medication obtained from the pharmacy and dispensed to subjects will be maintained by study personnel.

At each visit, the participant will be provided with a sufficient quantity of product for anticipated use and an additional 1 week of medication or given a 4 week card. This will allow the participant to have enough medication if the appointment is postponed. At the next visit, the participant will return unused medication, which will be recorded and redispensed as appropriate. Subjects will be monitored for adverse reaction using the same process as all other arms.

Patients will begin varenicline dosing one week before the day 15 quit date.

Starting Week: 0.5 mg once daily on days 1–3 and 0.5 mg twice daily on days 4–7.

Continuing Weeks: 1 mg twice daily for up to a total of 12 weeks.

Day	Days between visits+7	Daily dose	Tablets to be dispensed
Day 8 (W1) – visit	7 + 7 = 14	0.5 mg once daily for 3 days, then 0.5 mg twice daily for 4 days	22 tablets of 0.5 mg
Day 15 (W2) – visit	7 + 7 = 14	1 mg twice daily	28 tablets of 1 mg
Day 22 (W3) – visit	7 + 7 = 14	1 mg twice daily	28 tablets of 1 mg
Day 29 (W4) – visit	14 + 7 = 21	1 mg twice daily	42 tablets of 1 mg
Day 43 (W6) - visit	14 + 7 = 21	1 mg twice daily	42 tablets of 1 mg
Day 57 (W8) – visit	14 + 7 = 21	1 mg twice daily	42 tablets of 1 mg
Day 71 (W10) – BR2			Up to three weeks (21 tablets) to meet the FDA recommended duration

NRT dosing and dispensing (targeted, but may be revised as needed): Similar to the other conditions, NRT will be dispensed at each visit. Beginning at Day 8 (W1), the participant will be provided with a sufficient quantity of product for anticipated use and an additional 1 week of product. This will allow the participant to have enough

NRT if the appointment is postponed. At the next visit, the participant will return unused NRT, which will be recorded and redispensed as appropriate. Subjects will be monitored for adverse reaction using the same process as all other arms. The NRT will be distributed assuming the maximum allowed per day is 1 patch, 20 lozenges, and 24 pieces of gum.

**Day 8/ Wk1 visit:** One week after the baseline bronchoscopy, subjects will return (day 8) to report their tobacco and/or product use status, and to report any health issue. Subjects will be offered the opportunity to complete the questionnaires online and measure their breath CO within 24 hours before their scheduled visit. Subjects will complete questionnaires, and CO will be assessed. Blood pressure, heart rate, oxygen level and weight will be recorded.

Subjects in the SREC arms will be reminded that after one week of use as they learn to use the product and work towards complete substitution, they will begin their assignment effective on day 15. SREC users will be encouraged to use the product as frequently as needed to address cravings, allowed to smoke their usual brand of cigarettes *ad libitum* for another week, and encouraged to reduce their cigarettes per day to 5 or less, followed by quitting cigarette smoking and avoiding cannabis use. Subjects randomly assigned to the Complete Substitution with the placebo SREC device will be provided with appropriate dose/amount of varenicline and will be instructed to use it as indicated above.

Subjects randomized to NRT complete substitution will be provided patches in combination with gum and/or lozenge unless otherwise discussed, and instructed how to use these products. Dosing will be determined based on their baseline consumption and time to first cigarette. Subjects will be allowed to use a combination of products (e.g., patch and gum/lozenge) in order to achieve cessation. If subjects experience side effects, dosages can be reduced.

All subjects randomized to receive an intervention will receive counseling with motivational interviewing in order to achieve compliance.

Subjects who indicate difficulty maintaining a reliable source of communication (i.e., telephone, internet access) after enrolling in the study may be provided a cell phone to facilitate communication, data collection via internet, and improve retention. The cell phone and a data plan may be provided at no cost to the participant. Subjects will be instructed to return the phone at the end of the study. Phones will be erased and reused as needed. No data from the phone will be captured or retained.

**Day 15/ Wk 2, Day 22/ Wk 3, Day 29/ Wk4, Day 43/ Wk6 and Day 57/ Wk 8 visits (+/- 3 days):** Subjects in the intervention arms will begin their assignment (stop smoking) effective on day 15. Subjects will be offered the opportunity to complete the questionnaires online and measure their breath CO within 24 hours before each scheduled visit. At each visit, blood pressure, heart rate, oxygen level and weight will be recorded. Subjects will complete questionnaires. CO will be assessed. Subjects in the intervention groups will be asked to bring back their used and unused product and will be provided additional pods, varenicline and NRT as appropriate. Subjects who fail to return product or report daily use may be identified as non-compliant and removed from the study by the PI on a case by case basis. At day 57/Wk 8 visit, subjects will be given 24 hour urine collection containers and instructions. Subjects will receive a reminder to begin 24-hour urine collection the day before their bronchoscopy.

**Follow-up bronchoscopy:** At 10-weeks (8 weeks on the experimental condition and a 2 weeks run-in period), subjects randomized to the SREC groups will be instructed to use the assigned device immediately prior to the visit. During the visit, these subjects will demonstrate use and inhalation will be assessed in a closed room with negative pressure or a “smoke eater” device that will reduce the exposure to exhaled particles. Windows or webcams may be utilized to observe and communicate with participants during this exercise. No webcam images or audio data will be recorded or retained without the participants’ permission.

Inhalation of the SREC will be assessed by the Great Lakes Neurotechnology BioRadio System, which includes

2 respiration inductance plethysmography bands (thoracic and abdominal) and the VivoSense Advanced Respiratory Analysis Module and VivoSense Core Physiological Analysis Software. The subject's inhalation data will be recorded for approximately 2 minutes/15 breaths using a spirometer, then approximately 1 minute without the spirometer, before e-cig use, then while using e-cig for 10 puffs over 4.5 minutes, and lastly for an additional 1 minute after using the e-cig. A nicotine boost will be concurrently assessed for nicotine-SREC users (See below).

All subjects will undergo an additional bronchoscopy (the same procedure and measures as above). Subjects will be reminded that e-cigs are still a new product, and much is still unknown about the potential benefits of e-cigs for fostering smoking cessation, and the numerous types of harm that they could cause, both on an individual level and a population basis, and they will be advised not to use black market devices or modify commercial devices. Study staff will emphasize the importance of being e-cig and tobacco-free. If needed, subjects will be offered cessation services by referral to the national quit line ([name]). All subjects will be called within 72 hours post-bronchoscopy to monitor symptoms. All subjects will be called 3 months after study completion to assess their tobacco use, including e-cig use. Subjects are asked to return SREC devices and all unused product.

**Scheduling visits:** All visits and calls will have a small window (+/- 3 days) in which study procedures can be conducted without being recorded as a deviation.

**Compensation and Retention/Compliance Bonus:** Compensation will be provided weekly and/or at in-person visits using a reloadable ClinCard or similar method. Compensation listed below includes travel. If a subject reports transportation barriers for non-bronchoscopy visits, study staff will attempt to arrange alternative transportation (e.g., Lyft). Participants may have up to \$10 deducted from their visit compensation if the service is utilized and paid for by the study. Compensation for procedures and travel was determined by using existing studies (e.g., 2003H0142, 2015C0088, 2019C0082, 2020C0169) and consulting with several practitioners in the Pulmonary Department, as well as the DSMB.

Visit		Compensation
Orientation	Visit	\$60
Day 1 (W0) Bronchoscopy 1	Visit / procedure	\$250
Day 4	Call	\$5
Day 8 (W1)	Visit	\$40
Day 15 (W2)	Visit	\$40
Day 22 (W3)	Visit	\$40
Day 29 (W4)	Visit	\$40
Day 36 (W5)	Call	\$5
Day 43 (W6)	Visit	\$40
Day 50 (W7)	Call	\$5
Day 57 (W8)	Visit	\$40
Day 64 (W9)	Call	\$5
Day 71 (W10) Bronchoscopy 2	Visit / procedure	\$300
3 month follow-up	Call	\$10
RDS (Recruitment Referrals)		Up to \$60
Bonus (Daily CO, Random Visit)		Up to \$200
Total		Up to \$1140

**Bonus:** Subjects' at home CO daily monitoring (via iCO) and reporting will be incorporated into a contingency management bonus. Using a threshold of 6 ppm, subjects with CO levels  $\leq 6$  ppm  $\geq 5$  days per week will receive an additional \$20 per week (\$160 total). To address compensation equity among the conditions, subjects assigned to the usual brand smoking arm will be compensated if they send CO results  $\geq 5$  days per week.

Subjects will be eligible to receive a \$40 bonus at the end of the study if the BR2 urine sample confirms the subject followed study instructions for using the product, medication, or device as assigned **and** if all aspects of a randomly selected visit were completed (e.g., surveys, returned product and/or packaging, etc.). If the subject does not provide a 24 hour urine sample at BR2 or laboratory analysis indicates the subject did not follow study instructions, the bonus will not be provided. If the randomly selected visit is missed or instructions were not followed, it will be considered as “not following instructions” and the subject will not receive the bonus. The bonus will be given after the 3 month follow-up call or as appropriate (e.g., upon withdrawal).

**RDS:** Subjects may choose to invite individuals they believe to be smokers, age 21 years or older and who are willing to be screened to join the study. Subjects can earn \$10 for each person who meets those criteria and is phone screened. They can earn up to \$60 total. The RDS compensation was informed by another study using this approach (2017H0439) and aligns with the time and effort required.

If a subject is found to be ineligible at time of the procedure, the subject will be given \$25 for their time, plus \$7 for transportation or parking.

**Contacting subjects:** Subjects will be contacted up to 10 times over a 2 week window for participation, but no more than 3 voicemails requesting response will be left. Thus, if there is no option for voicemails, there will be up to 10 attempts during the day or evening. If unable to reach the participant, a letter will be sent asking for the participant to call us.

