duration extends the use up to one month after the intervention to be consistent with FDA-approved uses. [name] (or other MD associated with the study) will review all subjects' medical history and evaluate the subject for indications and safety of the varenicline at the BR1 visit prior to the procedure. Subjects may continue in the study if they are not eligible to use varenicline or refuses.

The medication (see below) will be obtained from the OSUWMC or James Cancer Center pharmacy in bulk. Medications will be stored at room temperature (as recommended by the manufacturer) and in locked cabinets.

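### The varenicline dispensing table disagrees with its own dosing text in two rows: the day-71 tablet count, and the strength of the day-8 reserve tablets

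*Protocol*

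**What the plan says.** The dosing text in Protocol section 4.c.i reads "Starting Week: 0.5 mg once daily on days 1–3 and 0.5 mg twice daily on days 4–7", followed by "Continuing Weeks: 1 mg twice daily for up to a total of 12 weeks". On timing it says "Patients will begin varenicline dosing one week before the day 15 quit date", which puts the first dose on study day 8.

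The supply rule is that at each visit the participant is "provided with a sufficient quantity of product for anticipated use and an additional 1 week of medication or given a 4 week card". The reason given for the extra week is "This will allow the participant to have enough medication if the appointment is postponed". Unused tablets are brought back, recorded and may be issued again.

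The table then lists a quantity for each visit. Its second column adds seven days to each between-visit interval. The day-8 row shows 7 + 7 = 14 days, a dose description that covers seven days, and "22 tablets of 0.5 mg". The rows for days 15 to 57 are all at 1 mg twice daily. The day-71 row has no interval, strength or daily dose, only "Up to three weeks (21 tablets) to meet the FDA recommended duration".

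The list of packs just above gives the starting 4-week card as 11 tablets of 0.5 mg and 42 tablets of 1 mg.

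**The concern.** The table turns the dosing text into tablet counts, so the two should agree row by row. In two rows they do not. At day 71 the count is half of what the text implies for the period named in the same cell. At day 8 the reserve week has no stated dose, and the tablets listed for it are of a strength that the text leaves behind after the first week.

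These are operative figures. The Day 8 visit description sends placebo-SREC participants back to this section for amount and instructions, and the dispensed quantity goes on the label. Staff working from the table and staff working from the text could hand out different supplies. A day-15 visit that falls late but inside the allowed three days would draw on the day-8 reserve, so that case is foreseeable.

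**Working it through.** All inputs come from the varenicline part of Protocol section 4.c.i. The check is tablets = days × tablets per day.

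**Rows at 1 mg twice daily (2 tablets a day)**

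| Row | Days covered | Days × 2 | Listed |
|---|---|---|---|
| Day 15 | 7 + 7 = 14 | 28 | 28 |
| Day 22 | 7 + 7 = 14 | 28 | 28 |
| Day 29 | 14 + 7 = 21 | 42 | 42 |
| Day 43 | 14 + 7 = 21 | 42 | 42 |
| Day 57 | 14 + 7 = 21 | 42 | 42 |
| Day 71 | up to three weeks = 21 | 42 | 21 |

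Five rows reproduce exactly. Day 71 does not.

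**Is three weeks the right remainder at day 71?** Twelve weeks is 84 days. From day 8 to day 71 is 71 − 8 = 63 days, so 84 − 63 = 21 days remain. The duration in the cell is consistent with the text; only the tablet count is not. At two a day, 21 tablets last 21 / 2 = 10.5 days. They last 21 days only at one a day, which the text does not give for the continuing weeks.

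**Can tablets already in hand explain the figure?**
- The day-57 reserve is 7 × 2 = 14 tablets. With it the participant holds 21 + 14 = 35, enough for 17.5 days. Put the other way, 42 − 14 = 28 would be needed, not 21.
- If every reserve were kept and nothing were netted off at reissue, the 1 mg tablets given out from day 15 to day 57 total 28 + 28 + 42 + 42 + 42 = 182. Use over the 56 days from day 15 to day 71 is 112, which leaves 70. That exceeds 42, so no further tablets would be needed.

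Neither route gives 21.

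**Day-8 row**
- Starting week as written: 3 × 1 + 4 × 2 = 11 tablets of 0.5 mg.
- Listed: 22 = 2 × 11, leaving 11 tablets of 0.5 mg for the reserve week.
- If the reserve week follows the continuing schedule: 11 tablets of 0.5 mg plus 7 × 2 = 14 tablets of 1 mg.
- If 0.5 mg twice daily simply continued: 3 × 1 + 11 × 2 = 25 tablets of 0.5 mg.
- If the starting 4-week card is given: 11 tablets of 0.5 mg for week one, then 42 / 2 = 21 days of 1 mg twice daily.

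The listed 22 matches only a repeat of the starting week, which the text does not describe. The loose-tablet route and the card route therefore supply different strengths for the second week of treatment.

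These counts are arithmetic on the Protocol's own schedule. They are not proposed quantities.

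**The case against.** The strongest defence is that the section presents its quantities as targets open to revision, ties supply to anticipated need, allows a 4-week card instead, and has unused tablets returned and reissued. Labels carry instructions for use, so a tablet count is not itself a dosing instruction. Giving the starting card avoids the day-8 gap altogether. All of this is fair, and it limits the consequence. It does not make the two rows agree with the text. The wording of the day-71 cell caps the duration, but the cell still equates three weeks with 21 tablets.

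A reader might also infer four stronger things, none of which the documents support:

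- **That 14 days of supply beside seven days of dosing is itself an error at day 8.** It is not; the extra week follows the stated rule. The problem is confined to the missing dose and the strength of the reserve tablets.
- **That day 71 is the only row not counted at two tablets a day.** Day 8 also departs from that count, because the starting week includes once-daily days.
- **That the table contradicts the stated duration.** The text says that the 12-week "duration extends the use up to one month after the intervention". Three weeks after day 71 completes the 12 weeks and lies within that ceiling.
- **That the second bronchoscopy data are affected.** The day-71 supply is for use after that procedure. The day-8 reserve would matter around day 15, eight weeks earlier, and nothing in the documents quantifies any carry-over to the samples.

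**Conclusion.** The point holds for two rows of one table. At day 71 the listed count is half of what the written schedule uses over the stated period, 21 against 42 tablets. At day 8 the reserve week has no stated dose, and its 11 tablets of 0.5 mg fit neither the move to 1 mg twice daily nor the alternative card.

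The day-71 result takes the twice-daily text as it stands. The text never mentions the reserve week by name, so applying the continuing schedule to it is an inference. The missing dose and the mismatch with the card do not depend on that inference.

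Varenicline is offered, and participants who decline it or are not eligible for it stay in the study. The 32 placebo-SREC participants are therefore an upper bound at day 8. Fewer would reach day 71 if retention is as planned: 66% of 32, about 21 per group (Protocol section 4.g.ii; SAP item 1). The matter is one of supply and participant care. No effect on power, alpha or the planned analysis is shown.

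**What to change.** The study physicians should reconcile the day-8 and day-71 rows with the dosing text and with the 4-week-card option, and reissue one consistent table. The day-71 row should state strength and daily dose as the other rows do, and the day-8 row should say what the reserve week is meant to contain. Which quantity or dose is correct is for the study physicians to decide; this review takes no position.

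The cost is a table correction in the next amendment, with a check of any labels or staff instructions made from the present table. No analysis changes.

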All intervention subjects will receive counseling with motivational interviewing in order to achieve compliance.

SREC Dispensing (targeted, but may be revised as needed): Participants will be provided two devices, in case one fails, including charging materials. Based on email and telephone conversations with the SREC manufacturer (NJOY), NIDA, and [name], a Cardiologist and Investigator at McGill University who is currently conducting a randomized clinical trial (Canadian E3 Trial) using a SREC device, we will assume that participants will use one tank/pod every two days (i.e., 0.5 tank/pod per day). At the anticipated rate, there will be 70 days on product or approximately 35 pods required.

Pods will be weighed and logged prior to dispensing. At each visit, the participant will be provided with a sufficient quantity of product for anticipated use and an additional 1 week of product. This will allow the participant to have enough product if the appointment is postponed or the participant uses more than anticipated. At the next visit, the participant will return used and unused product. Returned materials will be weighed. Unused/unopened product will be re-dispensed along with the necessary amount of new product. These estimates will vary depending on individual use. Dispensing will be adjusted to match product use. Participants can contact study staff to request additional product as needed. Participants will be asked to return all unused product and the devices at the end of the study.

Day	Days between visits 7	Pods to be dispensed*
Day 1 (W0) – BR1	7	7
Day 8 (W1) – visit	7	7
Day 15 (W2) – visit	7	7
Day 22 (W3) – visit	7	7
Day 29 (W4) – visit	14	11
Day 43 (W6) – visit	14	11
Day 57 (W8) – visit	14	11
Day 71 (W10) – visit	NA	

\*One week of additional product (~3 or 4 pods) may be distributed at each visit to provide sufficient quantity for any unanticipated use or delay in visit scheduling.

Varenicline dosing and dispensing (targeted, but may be revised as needed): Subjects randomly assigned to the Complete Substitution with the placebo SREC device will be offered up to 12 weeks of varenicline, a nicotinic receptor partial agonist indicated for use as an aid to smoking cessation treatment at no cost. The 12 week

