## d. Data Collection and Management Process

### i. Data to be collected

The schedule of measures is provided in Table 1.

**Baseline/orientation visit:** At the baseline visit, ideally less than two weeks before bronchoscopy, subjects will complete questionnaires, as indicated in Table 1. Exhaled CO , blood pressure, heart rate, oxygen level and height and weight will be assessed.

**Bronchoscopy visits:** At bronchoscopy visits, subjects will complete questionnaires, as indicated in Table 1. Blood pressure, heart rate, oxygen level and weight will be assessed. CO, FeNO and PFTs will be measured. General changes in diet and physical activity over the course of the study will be assessed at the second bronchoscopy visit. Product evaluation will be administered at the follow-up bronchoscopy to assess the experience with the SREC or NRT. Inhalation will be assessed at the follow-up bronchoscopy for subjects assigned to one of the e-cig use conditions, and a nicotine boost will be concurrently assessed for nicotine-SREC users. At the second bronchoscopy visit, the same measures will be provided. These measures are currently used in other studies, including a study involving bronchoscopy.

**Day 8/ Wk1, Day 15/ Wk 2, Day 22/ Wk 3, Day 29/ Wk4, Day 43/ Wk6 and Day 57/ Wk 8 visits:** At each in-person visit, subjects will complete questionnaires, as indicated in Table 1. Blood pressure, heart rate, oxygen level and weight will be assessed. CO will be measured. The product compliance, product accountability log and product evaluation scale will be used to assess the experience with the SREC or NRT.

Phone calls: During the weeks when there are no visits, subjects will be called on the phone to assess tobacco and/or product use, toxicity and health status. Subjects assigned to one of the intervention groups who need additional abstinence counseling beyond the planned visits and calls will be instructed to contact study staff. All subjects will be called within 72 hours post bronchoscopy to monitor symptoms and at 3 months after study completion to assess CESD, Expectancies, Drug Effects/Liking, stages of changes, FTND or modified FTND, as appropriate, product evaluation scale and their tobacco use, including e-cig use.

Daily tobacco use: Subjects will be asked to report their daily tobacco and/or product use by phone or internet.

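### The Day 71 row of the varenicline dispensing table gives 21 tablets for three weeks; at the stated 1 mg twice daily, three weeks is 42

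*Protocol*

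**What the plan says.** Protocol section 4.c.i offers varenicline to participants in the placebo-SREC arm, starting at the Day 8 visit. After a starting week on 0.5 mg tablets, the dose rule is "Continuing Weeks: 1 mg twice daily for up to a total of 12 weeks".

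A dispensing table then gives the tablets for each visit. The rows for Days 15 and 22 cover 14 days with 28 tablets of 1 mg. The rows for Days 29, 43 and 57 cover 21 days with 42 tablets. The Day 71 (BR2) row reads "Up to three weeks (21 tablets) to meet the FDA recommended duration".

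Other text in the same section bears on how the row would work in practice:

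- The section opens "Varenicline dosing and dispensing (targeted, but may be revised as needed", so the quantities are targets.
- The pack list includes "Starting 4-week card: 0.5 mg × 11 tablets and 1 mg × 42 tablets" and "Continuing 4-week card: 1 mg × 56 tablets".
- Each visit's supply is to cover expected use "and an additional 1 week of medication or given a 4 week card".
- At the next visit "the participant will return unused medication, which will be recorded and redispensed as appropriate".

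**The concern.** The Day 71 row contradicts both the dose rule above it and the other 21-day rows of its own table. It looks as if 21 days was written as 21 tablets. Staff who counted out loose tablets from the row would hand over half of what its stated duration requires. A participant relying on that supply would stop varenicline about ten days before the end of the 12-week course that the Protocol says it intends to make available. The stake is correct supply of a study medication, not the trial's comparisons.

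**Working it through.** **Inputs (all from Protocol section 4.c.i).** Start on Day 8; maximum duration 12 weeks; two 1 mg tablets a day from Day 15; BR2 on Day 71; table quantities and card contents as above.

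**Do the other rows follow the dose rule?** Tablets = days covered × 2.

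| Row | Days covered | Days × 2 | Table |
|---|---|---|---|
| Day 15 | 14 | 28 | 28 |
| Day 22 | 14 | 28 | 28 |
| Day 29 | 21 | 42 | 42 |
| Day 43 | 21 | 42 | 42 |
| Day 57 | 21 | 42 | 42 |
| Day 71 | 21 | 42 | **21** |

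The Day 8 row also reproduces: a starting week is 3 × 1 + 4 × 2 = 11 tablets of 0.5 mg, and two such weeks are 22, as listed. Only Day 71 fails.

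**Is the three-week duration right?** Last day of the course = 8 + 84 − 1 = Day 91. Days 71 to 91 inclusive are 21 days, so yes. The need is 21 × 2 = 42 tablets. If BR2 moves within its ±3-day window while the course still ends on Day 91, 18 to 24 days remain and the need is 36 to 48 tablets.

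**How long do 21 tablets last?** 21 / 2 = 10.5 days, so they run out on about Day 81.

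**Could carry-over explain 21?** That would require exactly 42 − 21 = 21 tablets in hand at Day 71. The Protocol does not say whether each row is a top-up to a total or all new supply, so both are tried, along with cards.

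- *Rows are totals that include returned tablets.* Of the 42 held from Day 57, 14 × 2 = 28 are used by Day 71, leaving 14. The new supply needed is 42 − 14 = 28. With 21 instead, the participant has 35 tablets, lasting 17.5 days to about Day 88, which is 7 short.
- *Rows are all new supply.* Dispensed from Day 15 to Day 57: 28 + 28 + 42 + 42 + 42 = 182. Used on Days 15 to 70: 56 × 2 = 112. Left: 70, more than the 42 needed, so nothing new is required.
- *4-week cards.* One starting and two continuing cards hold 42 + 56 + 56 = 154 tablets of 1 mg. The course needs 77 days (Days 15 to 91) × 2 = 154. The cards cover Days 8–35, 36–63 and 64–91. The third must be given at Day 57, because Day 64 is a phone call, and 56 − 14 = 42 tablets remain on it at Day 71. Nothing new is required.

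The new supply needed is therefore 42 with nothing carried forward, 28 with the one-week reserve, or 0. None of these is 21. Only one tablet a day gives 21, and that is not the stated regimen.

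**Size of the shortfall.** 21 tablets if the row is followed literally with nothing carried forward; 7 if the one-week reserve is in hand; none if 21 or more are carried forward or cards are used.

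**Participants.** At most 32 (the arm size); 32 × 0.66 ≈ 21 at the planned retention.

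**The case against.** The strongest reply is that this is a slip of the pen with little effect. The dose and the duration are both stated clearly and correctly, so nobody would change the regimen because of the row. The quantities are declared to be adjustable targets, supply is meant to be sufficient for expected use, leftovers are put back into use, and cards cover the full course exactly. Varenicline is also optional, and by this point the participant has had the second bronchoscopy.

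All of that stands, and it is why the point is minor. It does not make the number right. The row is an instruction to the staff who dispense, and no supply route in the section leads to 21.

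A reader might go further and infer that participants who take varenicline after BR2 are left without safety follow-up. The protocol body does schedule only two later contacts: "All subjects will be called within 72 hours post bronchoscopy to monitor symptoms and at 3 months after study completion to assess CESD", among other measures. For a full course, the days between the 72-hour call (by about Day 74) and Day 91 contain no scheduled call, and Table 1 has no column for the 72-hour call after BR2. The documents do not support calling this a defect:

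- Safety monitoring and adverse-event reporting are delegated to an attached Data Safety Monitoring Plan (DSMP), which is not among the documents and may provide for this period.
- Table 1 assigns the Adverse Events, Concomitant Medications and CESD forms to the 3-month call.
- Sections 4.f.i and 4.f.ii tell participants when to stop the drug, contact staff and seek care, and have study physicians evaluate suspected reactions.
- The 72-hour call is specified in the text, so its absence from Table 1 is a matter of tabulation.

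What remains is a question for the sponsor.

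**Conclusion.** The Day 71 quantity is wrong as written: it should be 42 tablets of 1 mg, and 21 is half of that. The result rests on the stated regimen of 1 mg twice daily, a Day 8 start, and BR2 on its nominal day.

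The point is minor. It would be an overreading to say that the arm will be under-supplied. A shortfall needs two conditions together: loose tablets counted from this row, and fewer than 21 carried forward. The Protocol gives no rates for accepting or continuing varenicline, so the number of participants who could be affected may be well below 32. The row concerns supply after the follow-up samples have been collected, so it has no bearing on the biomarker comparisons, the sample size or the SAP.

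**What to change.** Change the Day 71 entry to 42 tablets of 1 mg, less any tablets carried forward. This also settles the top-up question for that row and brings it into line with the card route, where the deduction leaves nothing to dispense. If BR2 falls off its nominal day, the same rule of two tablets per remaining day applies. A study physician should confirm the wording. The cost is one table entry, with no new visit, procedure or analysis.

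Separately, and only as a query: ask the sponsor to confirm that the attached DSMP covers adverse-event follow-up for participants who still have varenicline to take after BR2. If it does, nothing further is needed.
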